# VI- Comparison between the two groups regarding post delivery complain

[figure not shown]
The incidence of post-delivery complaint (HMB, Intermenstrual spotting and post coital bleeding) after 6 months was more in group I than group II, but it did not reach statistical significance. The most common complaint was spotting 8(61.5%) v.s 4(50%) followed by post coital bleeding 3(23.1%) v.s 2(25%).

So ,There was no statistical significant difference between two studied groups regarding post-delivery complain (P= 0.621, 0.102)

Post delivery complain	Gro	Group I		up II	P value
	No	%	No	%	
No	112	89.6	117	93.6	0.621
Yes	13	10.4	8	6.4	0.102
Spotting	8	61.5	4	50.0	0.071
НМВ	2	15.4	2	25.0	1.0
Post coital bleeding	3	23.1	2	25.0	0.92

Table (6): Post delivery complain in the two studied groups.

Group I. cesarean section with bladder dissection Group II: cesarean section without bladder dissection  $X^2$  = Chi square-test p was significant if  $\leq 0.05$ 

[figure not shown]

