## **Outcome measures:**

- 1. Incidence of occurrence of cesarean scar (cs) niche in each group.
- 2. Correlation between the depth of niche and the residual myometrium in each group.
- 3. Comparison between the thicknesses of residual myometrium to adjacent normal myometrium in each group.
- 4. Complains of niche if present.

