# RESULTS

This study was prospectively conducted on 250 women recruited from ElShatby university maternity hospital delivery ward; they were randomized into two groups group (A) and group (B) by closed envelop randomization.

Group (A) was undergo cesarean section with bladder dissection.

Group (B) was undergo cesarean section without bladder dissection.

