### II-Comparison between two groups as regard obstetric history

Gravidity in group I had mean value  $1.44\pm1.03$  and in group II had mean value  $1.312\pm0.737$ . Parity in group I had mean value  $0.136\pm0.68$  and in group II had mean value  $0.192\pm0.73$ . It was found that most of cases had no abortion in two studied groups 97(77.6%) and 99(79.2%) respectively. No ectopic cases was higher with 125(100%) and 124(99.2%) respectively. Gestational age had mean value  $37.41\pm2.37$  and in group II had mean value  $36.99\pm2.50$ .

[figure not shown]
There were no statistically significant differences between the two studied groups regarding gravidity (P = 0.133), parity (P = 0.069), abortion (P=0.465), ectopic (P=0.159) and gestational age (P = 0.175). (Table 2, Fig. 15)

[figure not shown]
Obstetric history	Group I	Group II	T test P value
Gravidity			
Range	1-9	1-6	0.133
Mean	1.44	1.312	0.155
SD	1.03	0.77	
Parity			
Range	0-6	0-4	0.069
Mean	0.142	0.192	0.009
SD	0.68	0.73	
Abortion			
No	97 (77.6%)	99 (79.2%)	0.465
1-2	27 (21.6%)	23 (18.4%)	0.403
>2	1 (0.8%)	3 (2.4%)	
Ectopic			
No	125(100.0%)	124 (99.2%)	0.159
Yes	0.0 (0.0%)	1 (0.8%)	
Gestational age			0.175

[figure not shown]
Table (2): Comparison between the two studied groups regarding obstetric history.

Range	34-41	33-41	
Mean	37.41	36.99	
SD	2.37	2.50	

Group I. cesarean section with bladder dissectiont-test = student t-testGroup II: cesarean section without bladder dissection p was significant if  $\leq 0.05$ 

[figure not shown]

Figure (15): Comparison between the two studied groups regarding obstetric history.

[figure not shown]

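### Table 6 compares the arms on symptom percentages whose base shifts, unlabelled, from 125 women per arm to the 13 v 8 complainers, and its symptom P values follow no single reproducible rule

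*SAP*

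**What the plan says.** The protocol lists complaints as its fourth outcome, "Complains of niche if present", and fixes no denominator or test for it; its Results section promises only standard methods.

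The SAP reports the outcome at six months in section VI and Table 6. The first two rows cover every woman in each arm: "No 112 89.6 117 93.6 0.621" and "Yes 13 10.4 8 6.4 0.102" (columns: group I number and percent, group II number and percent, P). Group I had bladder dissection and group II did not.

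Three symptom rows follow in the same columns. Two of them read "Spotting 8 61.5 4 50.0 0.071" and "Post coital bleeding 3 23.1 2 25.0 0.92"; the HMB row gives 2 (15.4%) v 2 (25.0%), P 1.0. The text repeats two of the three comparisons: "The most common complaint was spotting 8(61.5%) v.s 4(50%) followed by post coital bleeding 3(23.1%) v.s 2(25" (the quote stops just before the closing percent sign). The table footnote names the chi-square test at the 0.05 level. It does not mention a continuity correction or a change of base.

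**The concern.** A percentage in a two-arm table is normally read as the proportion of that arm with the event. In Table 6 this is true of the first two rows and not of the next three. Complainers are a subset formed after randomisation, and there are more of them in group I (13) than in group II (8). Dividing by them puts the same number of events at a lower percentage in group I, so the symptom percentages do not compare the randomised arms.

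The P column raises a second problem. Its symptom values should all come from one test on one base, and they do not appear to. At stake is whether a reader can take symptom incidence, and the strength of evidence for a difference, from the table for a listed outcome. Complaints are the only outcome in the list that women themselves report.

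**Working it through.** **Inputs.** SAP Results: "This study was prospectively conducted on 250 women recruited from ElShatby university maternity hospital delivery ward". Arm sizes of 125 and 125 follow from SAP section II, "No ectopic cases was higher with 125(100%) and 124(99.2%) respectively", since 124/125 = 99.2%. They also follow from Table 6 itself: 112 + 13 = 125 and 117 + 8 = 125. Symptom counts from Table 6 are spotting 8 v 4, HMB 2 v 2, post-coital 3 v 2. They sum to the complainers: 8 + 2 + 3 = 13 and 4 + 2 + 2 = 8.

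**Step 1: reproduce the printed percentages, then change the base.**

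| Row | Base 13 v 8 (as printed) | Base 125 v 125 |
|---|---|---|
| Spotting | 8/13 = 61.5% v 4/8 = 50.0% | 6.4% v 3.2% |
| HMB | 2/13 = 15.4% v 2/8 = 25.0% | 1.6% v 1.6% |
| Post-coital | 3/13 = 23.1% v 2/8 = 25.0% | 2.4% v 1.6% |

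All six printed symptom percentages reproduce on 13 and 8. Per woman, the HMB difference disappears, the post-coital direction reverses, and the spotting direction is unchanged.

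**Step 2: try to reproduce the P values.** For a two-by-two table with events a and c, non-events b and d, arm sizes n1 and n2, totals with and without the event m1 and m0, and N women in all, uncorrected X² = N(ad − bc)² / (n1·n2·m1·m0), on 1 degree of freedom.

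On 125 v 125:
- Spotting: 250 × (8×121 − 117×4)² / (125×125×12×238) = 1.401, P = 0.237
- HMB: X² = 0, P = 1.0
- Post-coital: 250 × (3×123 − 122×2)² / (125×125×5×245) = 0.204, P = 0.651

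On 13 v 8:
- Spotting: 21 × (8×4 − 5×4)² / (13×8×12×9) = 0.269, P = 0.604
- HMB: 21 × (2×6 − 11×2)² / (13×8×4×17) = 0.297, P = 0.586
- Post-coital: 21 × (3×6 − 10×2)² / (13×8×5×16) = 0.010, P = 0.920

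| Row | Printed P | 125 v 125 | 13 v 8 |
|---|---|---|---|
| Spotting | 0.071 | 0.237 | 0.604 |
| HMB | 1.0 | 1.0 | 0.586 |
| Post-coital | 0.92 | 0.651 | 0.920 |

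The Yates-corrected, likelihood-ratio, unpooled z and Fisher tests were also tried. None gives both 1.0 for HMB and 0.92 for post-coital bleeding on one base. None gives 0.071 for spotting on either base; the smallest one-sided value found is about 0.118.

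**Step 3: which test suits the corrected rows.** The expected count per arm on 125 v 125 is half the row total: spotting 12/2 = 6, HMB 4/2 = 2, post-coital 5/2 = 2.5. Chi-square is usable for spotting. The other two rows are too sparse for it. Fisher P values are 0.376 (spotting), 1.0 (HMB) and 1.0 (post-coital).

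**Step 4: sensitivity to the base.** Table 4 accounts for 89 + 35 = 124 women in group I. On 124 v 125, group I becomes 8/124 = 6.45%, 2/124 = 1.61% and 3/124 = 2.42%, each within 0.1 point of the figures above. Spotting becomes P = 0.231 (Fisher 0.254) and post-coital bleeding Fisher 0.684, so the exact P values depend on settling the base, but none approaches 0.05.

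**The case against.** The best defence is that the quoted sentence ranks complaint types, and a share of complainers is the right figure for a ranking. The symptom rows follow the Yes row and sum to it, so they can be read as a breakdown. Table 7 uses the same subset and labels it with 13 and 8. The counts also stand beside the percentages. This all stands: no percentage is miscalculated, and as a description the shares are legitimate. It does not cover placing them, unlabelled, in the columns that hold per-arm percentages and attaching between-arm P values.

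A reader might infer that the SAP claims HMB and post-coital bleeding are commoner without dissection, or that spotting came close to significance. It claims neither. Section VI says that complaints were more frequent in group I, without significance. Only post-coital bleeding reverses, and that rests on one woman (3 v 2).

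A reader might also take it as established that the P values mix denominators. That is an inference. The Yates test on 13 v 8 also gives 1.0 for HMB, in which case the column would mix tests. Neither account explains 0.071.

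Finally, the protocol's outcome could mean complaints among women with a niche (35 v 26 in Table 4). The documents do not say how many complainers had a niche, and Table 6 covers 125 per arm. If every complainer had one, uncorrected chi-square would give 0.468, 0.758 and 0.902 for the three rows, which matches none of the printed values.

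**Conclusion.** The point holds as a reporting error in Table 6. The base changes without a label, and the symptom shares do not compare incidence between randomised arms. An apparent HMB gap of 9.6 points (25.0 − 15.4) is zero per woman, and an apparent post-coital deficit of 1.9 points with dissection (25.0 − 23.1) is an excess of 0.8 points (2.4 − 1.6). The spotting P value of 0.071 cannot be reproduced on either base, and 0.92 belongs to the complainer subset under uncorrected chi-square.

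The consequence is limited. No symptom difference is significant on either base, and no conclusion stated in the text changes. The result assumes that all 125 women in each arm were assessed for complaints, as Table 6 implies. It is separate from the fact that the No and Yes rows carry two P values (0.621 and 0.102) for what is one contrast; correcting that would leave these three rows as they are.

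**What to change.** In Table 6 and its text, give the symptom rows over the women assessed in each arm:

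- Spotting 8 (6.4%) v 4 (3.2%). Replace 0.071 with the named chi-square result, 0.237; Fisher 0.376 is an acceptable alternative.
- HMB 2 (1.6%) v 2 (1.6%), P stays 1.0.
- Post-coital bleeding 3 (2.4%) v 2 (1.6%). Replace 0.92 with Fisher 1.0 and state the test in the footnote.

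Confirm first that 125 women were assessed in each arm, since Table 4 accounts for 124 in group I; if the base differs, recompute these rows. If the shares of complainers are kept to show which complaint was commonest, head them n=13 and n=8, call them descriptive, and give no P value.

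The cost is a re-tabulation of counts already printed, a footnote and one sentence of text. No new data are needed beyond confirming the number assessed.

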# Figure (19): Post delivery complain in the two studied groups

# VII- Comparison between the two groups regarding incidence of postdelivery complaint and the type of contraceptive used

It was found that the highest incidence of complaint in both groups was found in cases with no contraceptive, followed by IUD user. There was statistical significant difference between two studied groups regarding complaint incidence in non contraceptive-user (P=0.036) (Table 7, Fig. 20)

Table (7): Relation between the incidence of post delivery complication and the type of contraceptive used.

		up I 13″		Group II P va "n=8"	
	No	%	No	%	
No	7	46.2	5	62.5	0.036*
IUD	3	23.1	2	25.0	0.521
Pops	1	7.7	0	0.0	-
COCS	1	7.7	0	0.0	-
Depoprovera	1	7.7	1	12.5	1.0

**Figure (20):** Relation between the incidence of post delivery complication and the type of contraceptive used.

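### Table 6 reports two P values (0.621 and 0.102) for one yes/no complaint outcome; the stated chi-square test on the printed counts gives 0.254

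*SAP*

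**What the plan says.** Section VI of the SAP document compares complaints after delivery between group I (bladder dissection) and group II (no dissection). Table 6 opens with two rows, each with its own P value: "No 112 89.6 117 93.6 0.621" and "Yes 13 10.4 8 6.4 0.102". The text gives the same pair: "There was no statistical significant difference between two studied groups regarding post-delivery complain (P= 0.621, 0.102"). The note under the table names the test: "Chi square-test p was significant if" at or below 0.05. It says nothing about a continuity correction or sidedness.

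The text says that complaints "after 6 months was more in group I than group II, but it did not reach statistical significance".

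Three symptom rows follow. The text gives two of them as "The most common complaint was spotting 8(61.5%) v.s 4(50%) followed by post coital bleeding 3(23.1%) v.s 2(25"%). Table 6 prints P values of 0.071 for spotting, 1.0 for heavy menstrual bleeding (HMB) and 0.92 for post-coital bleeding. The text repeats none of these three.

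**The concern.** A woman either has a complaint or does not. If both rows count the same women, testing one row is the same as testing the other, and two different P values cannot both be right. Because the pair is in the sentence as well as the table, a misread table cell does not explain it.

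The protocol's outcome list includes "Complains of niche if present", so this is a listed outcome, and a reader cannot tell which P value belongs to it.

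The symptom rows raise a second, less certain question. Their percentages are shares of complainers, whereas the two rows above are shares of all women, and Table 6 does not mark the change. A printed P of 0.071 for spotting also looks close to significance, which the counts do not support.

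**Working it through.** **Inputs.** Table 6: complaint 13 v 8; no complaint 112 v 117; spotting 8 v 4; HMB 2 v 2; post-coital bleeding 3 v 2. The SAP document's opening paragraph gives 250 women in total.

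**Are the two rows one table?** 112 + 13 = 125 and 117 + 8 = 125, together 250. The percentages also add up: 89.6 + 10.4 = 100 and 93.6 + 6.4 = 100. The symptoms sum to the complaint row: 8 + 2 + 3 = 13 and 4 + 2 + 2 = 8. The rows are complements.

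**Stated test.** X² = N(ad − bc)² / (product of the four margins) = 250 × (13 × 117 − 112 × 8)² / (125 × 125 × 21 × 229) = 250 × 625² / 75,140,625 = 1.300 on 1 df, P = 0.254. Swapping the rows gives the same value. The smallest expected count is 21 × 125/250 = 10.5, so the test is adequate.

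**Can the printed values be reproduced?** P = 0.621 needs X² = 0.244, and P = 0.102 needs X² = 2.674. The alternatives tried were:

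| Method | P |
|---|---|
| Chi-square, uncorrected | 0.254 |
| Chi-square, one-sided | 0.127 |
| Yates correction | 0.362 |
| Fisher's exact, two-sided | 0.362 |
| Likelihood ratio | 0.252 |
| Barnard | 0.294 |
| t-test on 0/1 data | 0.256 |
| 112 v 117 alone against 1:1 | 0.741 |
| 13 v 8 alone against 1:1 | 0.275 |
| Chi-square, niche-positive women as denominators (35 and 26) | 0.604 |

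None gives 0.621 or 0.102.

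**Effect size.** Risk difference = 13/125 − 8/125 = 10.4% − 6.4% = 4.0 points. The Wilson limits are 0.0618 to 0.1698 (group I) and 0.0328 to 0.1212 (group II). Newcombe's method combines them:
- Lower limit: 0.040 − √[(0.104 − 0.0618)² + (0.1212 − 0.064)²] = −0.031.
- Upper limit: 0.040 + √[(0.1698 − 0.104)² + (0.064 − 0.0328)²] = 0.113.

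**Symptom rows.** The printed percentages are shares of complainers: 8/13 = 61.5% and 4/8 = 50.0%.

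| Symptom | Printed P | Chi-square, 125 per arm | Chi-square, complainers | Yates, complainers | Fisher, 125 per arm | Smallest expected count (125 per arm) | Difference over 125, points (Newcombe 95% CI) |
|---|---|---|---|---|---|---|---|
| Spotting | 0.071 | 0.237 | 0.604 | 0.948 | 0.376 | 6.0 | 3.2 (-2.5 to 9.2) |
| HMB | 1.0 | 1.0 | 0.586 | 1.0 | 1.0 | 2.0 | 0.0 (-4.2 to 4.2) |
| Post-coital bleeding | 0.92 | 0.651 | 0.920 | 1.0 | 1.0 | 2.5 | 0.8 (-3.5 to 5.4) |

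Post-coital bleeding matches the uncorrected test among complainers. HMB does not match that test, but it matches 125 per arm, or Yates among complainers. Spotting matches none of these. No one test and denominator among those tried yields all three.

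**The case against.** The best counter-argument accepts the duplicated P value and limits what is attached to it.

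- **Continuity correction.** The note does not say whether the chi-square was corrected, and with Yates the answer would be 0.362. This stands as a reason to name the variant. Either way there is one P value, and it is neither printed figure.
- **Spotting digits.** The 0.071 is in a table cell only, with no sentence to confirm it. This stands: what is said about that figure depends on a check of the source.
- **Choice of Fisher for spotting.** The smallest expected count is 6.0, so chi-square (0.237) would be acceptable there, and comparing 0.071 with Fisher's 0.376 makes the gap look wider. That is fair. Fisher is suggested for all three symptoms so that one method is used, because the other two have expected counts below 5. Spotting is far from 0.071 on either test.
- **Denominators.** A reader can work out 8/13 and 4/8, and the printed 1.0 and 0.92 each fit some test. This stands: for those two rows the basis is unclear, but error is not shown.
- **Importance.** Complaints come last of four listed outcomes and no conclusion changes. That limits the weight of the point but does not make the printed figures right.

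**Conclusion.** The point holds. Table 6 and its text give two incompatible P values for one binary outcome, and neither follows from the printed counts. Taking those counts as correct, and reading the note as the uncorrected two-sided chi-square, the single value is 0.254. That at least one printed value is wrong does not depend on the choice of test.

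The symptom P values have no single evident basis and are less certain, since they rest on table cells alone. No recalculated two-sided P value is below 0.05, so the stated conclusion of no significant difference in complaints is unaffected. The interval of -3.1 to 11.3 points tells the reader more than either printed P value.

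**What to change.** - In Table 6 and the sentence in section VI, replace 0.621 and 0.102 with one chi-square P value of 0.254, stated as uncorrected, and add the risk difference of 4.0 points (Newcombe 95% CI -3.1 to 11.3).
- Keep the complainer-only percentages as description, labelled n=13 and n=8 and without P values. The column heads of Table 7 ("Relation between the incidence of post delivery complication and the type of contraceptive used") already carry these denominators.
- If symptoms are compared between arms, use 125 per arm and Fisher's exact test: spotting 0.376, HMB 1.0, post-coital bleeding 1.0. Use Newcombe intervals if any are given.
- Check the printed 0.071, 1.0 and 0.92 against the source output.

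The cost is re-running one table from counts already printed, correcting one sentence and adding a denominator label. No new data are needed and the stated conclusion stays as it is.

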# Figure (19): Post delivery complain in the two studied groups

# VII- Comparison between the two groups regarding incidence of postdelivery complaint and the type of contraceptive used

It was found that the highest incidence of complaint in both groups was found in cases with no contraceptive, followed by IUD user. There was statistical significant difference between two studied groups regarding complaint incidence in non contraceptive-user (P=0.036) (Table 7, Fig. 20)

Table (7): Relation between the incidence of post delivery complication and the type of contraceptive used.

		up I 13″		Group II P va "n=8"	
	No	%	No	%	
No	7	46.2	5	62.5	0.036*
IUD	3	23.1	2	25.0	0.521
Pops	1	7.7	0	0.0	-
COCS	1	7.7	0	0.0	-
Depoprovera	1	7.7	1	12.5	1.0

**Figure (20):** Relation between the incidence of post delivery complication and the type of contraceptive used.

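### Table 7's significant arm difference in complaints among women using no contraception (P=0.036) cannot be reproduced from its counts, and the table has no denominators for an incidence

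*SAP*

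**What the plan says.** Section VI of the SAP (Table 6) gives the number of women with any post-delivery complaint in each arm: "Yes 13 10.4 8 6.4 0.102". With the women who had none (112 and 117), each arm totals 125. The overall comparison is reported as not significant, and no P value in Table 6 is starred.

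Section VII (Table 7) takes those 13 and 8 women and splits them by contraceptive method. The row for no method reads "No 7 46.2 5 62.5 0.036", with an asterisk on the P value. The remaining counts (group I, group II) are IUD 3 and 2, progestogen-only pills 1 and 0, combined pills 1 and 0, and Depo-Provera 1 and 1.

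The text draws two conclusions from this table. The first ranks the methods: "It was found that the highest incidence of complaint in both groups was found in cases with no contraceptive, followed by IUD user". The second compares the arms: "There was statistical significant difference between two studied groups regarding complaint incidence in non contraceptive-user (P=0.036").

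Table 7 names no test. The footnote to Table 6 names the chi-square test at the 0.05 level and does not state sidedness.

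**The concern.** Two things look wrong. First, 7 of 13 and 5 of 8 are similar proportions in very small groups, so a P value of 0.036 is not credible on sight. The percentage printed beside the 7 also does not match it.

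Second, both sentences speak of incidence, but the table's base is women who already have a complaint. The share of complainers who use no method depends heavily on how many women use no method. It says nothing about the risk of a complaint among non-users unless the number of non-users is known.

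Complaints are the fourth outcome in the protocol's list of outcome measures, and this is the only starred symptom result in the SAP. A reader could take it to mean that bladder dissection affects bleeding complaints in women who use no contraception.

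**Working it through.** **Inputs.** Complainers: 13 and 8 (Table 6, repeated as the column bases of Table 7). Complainers using no method: 7 and 5 (Table 7). Women per arm: 112 + 13 = 125 and 117 + 8 = 125 (Table 6). Two-sided tests are assumed.

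**Internal check of the group I column**

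- Counts: 7 + 3 + 1 + 1 + 1 = 13, which matches the base.
- Percentages: 46.2 + 23.1 + 3 × 7.7 = 92.4, which does not reach 100.
- 7/13 = 53.8%; 6/13 = 46.2%.

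The count fits its column and the percentage does not, so the percentage is the likelier error. Both versions are tested below.

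**Attempt to reproduce P=0.036.** For a 2×2 table with cells a, b (group I) and c, d (group II), chi-square = N(ad − bc)² / [(a+b)(c+d)(a+c)(b+d)].

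- 7/13 v 5/8: 21 × (7×3 − 6×5)² / (13 × 8 × 12 × 9) = 1,701 / 11,232 = 0.151
- 6/13 v 5/8: 21 × (6×3 − 7×5)² / (13 × 8 × 11 × 10) = 6,069 / 11,440 = 0.531
- 7/125 v 5/125: 250 × (7×120 − 118×5)² / (125 × 125 × 12 × 238) = 15,625,000 / 44,625,000 = 0.350
- IUD, 3/13 v 2/8: 21 × (3×6 − 10×2)² / (13 × 8 × 5 × 16) = 84 / 8,320 = 0.010

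| Comparison | Printed P | Chi-square P | Fisher P |
|---|---|---|---|
| No method, 7/13 v 5/8 | 0.036 | 0.697 | 1.00 |
| No method, 6/13 v 5/8 | 0.036 | 0.466 | 0.659 |
| No method, 7/125 v 5/125 | 0.036 | 0.554 | 0.769 |
| IUD, 3/13 v 2/8 | 0.521 | 0.920 | 1.00 |

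The smallest expected count in the first comparison is 8 × 9 / 21 = 3.4, so Fisher's test is the better choice there; the conclusion is the same.

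Other routes were tried for 7/13 v 5/8: Yates correction (1.00), one-sided chi-square (0.349), likelihood ratio (0.70), unpooled Wald (0.694) and Barnard (0.76). A goodness-of-fit test of 7 against 5 gives 0.564, and the whole 2×5 table gives 0.84. Entering the printed percentages as if they were counts out of 100 gives 0.021, or 0.030 with Yates. That is not a valid analysis, and it still does not give 0.036.

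**Direction.** The share of complainers using no method is higher in group II (62.5% v 53.8%), while the count is higher in group I (7 v 5). The sentence does not say which arm is worse.

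**Could the missing denominators produce 0.036?** The incidence comparison is 7/m against 5/n, where m and n are the unreported numbers of non-users. These are assumed values; P is uncorrected chi-square.

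| m v n | Ratio of larger to smaller | P |
|---|---|---|
| 20 v 20 | 1.0 | 0.49 |
| 100 v 100 | 1.0 | 0.55 |
| 7 v 7 (smallest P for any equal totals) | 1.0 | 0.127 |
| 7 v 10 | 1.4 | 0.026 |
| 10 v 18 | 1.8 | 0.031 |
| 15 v 30 | 2.0 | 0.032 |
| 24 v 50 | 2.1 | 0.036 |
| 30 v 64 | 2.1 | 0.036 |
| 15 v 5 | 3.0 | 0.035 |

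Equal totals never give significance. Where group I has 15 or more non-users, reaching 0.036 with the excess risk in group I takes about twice as many non-users in group II. Smaller ratios suffice only at very small totals; at 7 v 10, every non-user in group I would have to have complained.

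**The case against.** The strongest reply is that 0.70 is not the correct P value for the sentence as worded. The sentence is about incidence among non-users, whereas 7/13 v 5/8 compares shares of complainers. The true P value cannot be calculated from the documents, and with suitable totals it could be 0.036. This stands: 0.70 is the result for the shares the table displays, not a replacement incidence P value.

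Contraception is also chosen after delivery, so randomisation does not guarantee similar numbers of non-users in the two arms. This stands too. A two-fold gap between arms of 125 would be surprising, but that is a judgement, and such a gap would itself need to be reported.

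The result concerns 21 women in a breakdown that the protocol does not plan. It is remote from the niche comparison, and the SAP does not state a causal claim. All true, and no primary result changes. The sentence nevertheless asserts significance in the text on figures that do not show it.

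Finally, the ranking sentence may be loose wording for where most complaints occurred. Read that way it agrees with the counts (7 and 5, then 3 and 2), and rewording would settle it.

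**Conclusion.** The concern holds. No valid test on the displayed counts gives P=0.036 or any value below 0.05. The shares shown give P=0.70 (Fisher 1.00), the alternative count of 6 gives 0.47, and the whole-arm bases give 0.55. The printed IUD P value of 0.521 is not reproduced either (0.92), and the 7 and the 46.2% cannot both be right. An incidence by method cannot be calculated, because the number of women using each method is not given.

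These results assume two-sided tests and 125 women per arm. Unreported and markedly unequal numbers of non-users could yield 0.036, so the claim is unsupported by the data shown rather than proven impossible. Because it is the only symptom finding marked significant, it must be corrected before the results are used.

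**What to change.** If contraceptive use was recorded for every woman, rebuild Table 7 with complaints over all users of each method in each arm (x of N), test with Fisher's exact test, and rewrite both sentences from the result. Print the totals whatever the P value.

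If it was not recorded, delete the P values in Table 7 and both incidence sentences, and present the counts descriptively as the methods used by women who complained.

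In either case, check source data to settle whether the first group I entry is 7 (53.8%) or 6 (46.2%). If it is 6, the column then totals 12, and the thirteenth woman must be accounted for.

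The cost is one cross-tabulation, or the removal of two sentences and a column of P values. What is lost is one result marked significant, which the table does not support.
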